9.3.5 Data imputations

Missing values will not be imputed since for every analysis an observed-cases approach will be applied.

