1. INTRODUCTION

The purpose of this document is to provide further details about the statistical analysis methods specified in study protocol for the Phase I Dose Escalation Study of MEN1309, a CD205 Antibody-Drug Conjugate, in Patients with CD205-Positive Metastatic Solid Tumors and Non-Hodgkin Lymphoma.

The study is sponsored by Menarini Ricerche S.p.A

MEN1309 solution for infusion. MEN1309 will be administered by a 3-hour intravenous (IV) infusion on Day 1 of a 21-day cycle.

In Step 1 (investigation in Solid Tumors), MEN1309 cohort ascending doses start from 0.05 mg/kg up to 3.36 mg/kg. Study drug is given until objective disease progression is documented or another criterion for discontinuation [i.e., protocol violation, a dose-limiting toxicity (DLT), a serious adverse event (SAE), a patient receives other treatment, pregnancy, or withdrawal of consent] is met. Once the maximum tolerated dose (MTD) is determined in solid tumors, patients with locally advanced and metastatic triple negative breast cancer (TNBC) will be enrolled aiming to administer MEN1309 to 25 patients at the MTD (Expansion Phase).

In Step 2 (investigation in Non-Hodgkin's Lymphoma-NHL), escalating dose levels is based upon experience gained during Step 1 solid tumors, i.e. Step 2 is intended to run in parallel with Step 1 but at a lower dose level, so that the cohorts of patients with NHL in Step 2 cannot exceed at any time the doses tested in solid tumors during the dose escalation.

MEN1309-01 cohorts potentially run in parallel at the same dose level only at the MTD. By the end of the study one patient has been treated at 0.08 mg/Kg.

At the time Protocol Version 3.0 was implemented, the dose cohort of 1.60 mg/kg was successfully completed in Step 1, therefore the dose escalation in Step 2 started at 0.80 mg/kg. In Step 2, study drug will be given until objective disease progression is documented or until any other criterion for discontinuation is met, for a maximum number of 8 cycles. Beyond the 8th cycle, further cycles may be allowed for patients who still benefit from the treatment based upon the Investigator's medical judgement and medical monitor approval.

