Demographic and baseline characteristics, including age, gender, race will be summarized by cohort. All demographic data recorded on the eCRF will be listed.

Medical History and Concurrent Medical Conditions

Medical history will be coded using the Medical Dictionary for Regulatory Activities (MedDRA version 15.1). The number of patients with at least one recorded medical history or current medical condition will be presented using frequency counts and percentages as well as an incidence table by System Organ Class (SOC) and Preferred Term (PT). The safety population will be used for this summary. Details of medical history will be provided in listings.

Safety Analyses

Safety evaluations will be performed using the safety population.

Adverse Events

AEs will be categorized as Treatment-Emergent Signs and Symptoms (TESS) or Non-TESS for each of the study periods defined below. If an AE occurs for the first time or if it worsens in terms of seriousness or severity after the first study drug intake, it will be classified as TESS, otherwise it will be classified as non-TESS. Each adverse event will be classified according to the grade (Grade 1 to 6) depending on severity of the event, as specified in Section 8.6.1.5 of the Study Protocol.

The following periods are defined for assignment of TESS:

- Cycle 1: date of the administration to the day before the administration of Cycle 2 or, if the subject is discontinued, until the end of study.
- Cycle n: date of the administration to the day before start of Cycle n+1.

The following rule will be applied for each period: Period start date \leq AE start date \leq Period stop date.

The maximum relationship to study drug will be reported for the respective summaries. All AEs summaries will be based on the Safety population.

In particular grade ≥ 2 ADR will be listed since the occurrence of grade ≥ 2 ADR is associated with the switch from an ATD design to a 3+3 design.

The intensity of an adverse event is reported on the eCRF using the following definitions:

- **Mild:** It does not interfere with routine activities;
- **Moderate:** It interferes with routine activities;
- **Severe:** It makes it impossible to perform routine activities.

The maximum intensity will be used for the summaries; all events will be included in the listings.

Missing intensity will be left as missing and categorised as such.

Serious Adverse Events (SAEs) are defined in Section 8.6.3 of the Study Protocol

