A Treatment-Emergent SAE is defined as a TESS event classified as serious.

An AE will be classified as related to study drug if causality was recorded as “certainly related”, “probably related”, “possibly related”, “unassessable/unclassifiable”. Missing causality will be considered as related.

An overview of TESS will be provided with the number and percentage of patients reporting an event by cohort and overall for each period. The summaries will be presented for the following categories:

- Any TESS

- Any TESS by grade (<2, >=2)
- Any Serious TESS
- Any mild/moderate/severe TESS
- Any TESS leading to study drug discontinuation
- Any TESS leading to temporary study drug administration interruption
- Any related TESS (by categories)

If a patient has more than one occurrence of a TESS, the patient will be counted only once within that preferred term. The same applies to serious TESSs and drug-related TESSs.

Additionally, the following summaries of TESSs expressed as number and percentage of patients with TESSs will be presented by SOC and PT by cohort and overall, for each period:

- TESS
- Serious TESS
- Serious TESS resulting in death
- TESS of Grade >=2
- TESS of Grade <2
- TESS by intensity (by categories)
- TESS leading to study drug discontinuation
- Serious TESS leading to study drug discontinuation

Drug-related TESSs will be summarized in the same way that TESS as it is described above.

Moreover, the following summary will be presented for drug-related TESS:

- Number of events, number of patients and percentage of patients with DLT by SOC and PT

In the final TFL a summary of TESSs by period and Grade will be reported.

All adverse events (including non-TESS or AEs happening after End of Study Visit of the patient) recorded on the eCRF will be listed. A separate list of serious adverse events will be provided. TESS will be flagged in the listings.

Laboratory data

All laboratory data will be listed.

Clinical chemistry, haematology and urinalysis parameters will be summarized by parameter, visit and cohort using descriptive statistics. The change from baseline will be summarized for each post baseline visit with descriptive statistics by cohort and visit.

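### There is no rule for incomplete adverse event start dates: undated events fall outside the treatment-emergent and by-period tables, and most month-only dates cannot be placed in a 21-day cycle

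*Protocol*

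**What the plan says.** - Protocol 9.3.5 covers missing data in one sentence: "Missing values will not be imputed since for every analysis an observed-cases approach will be applied".
- SAP 6.1.1.2 (Adverse Events) classes an AE that first occurs, or worsens, "after the first study drug intake, it will be classified as TESS, otherwise it will be classified as non-TESS". The classification is made for each study period.
- A period is assigned by a date comparison. "The following rule will be applied for each period": the AE start date must be no earlier than the period start and no later than the period stop.
- Cycle 1 runs from the "date of the administration to the day before the administration of Cycle 2 or, if the subject is discontinued, until the end of study". Each later cycle runs to the day before the next one starts. The planned cycle is 21 days (SAP 1: "MEN1309 will be administered by a 3-hour intravenous (IV) infusion on Day 1 of a 21-day cycle").
- The main tables follow these periods: "An overview of TESS will be provided with the number and percentage of patients reporting an event by cohort and overall for each period". The tables by system organ class and preferred term are also for each period. The DLT summary sits under drug-related TESS and is not stated to be by period.
- Other missing AE fields have a rule. For relationship to drug, "Missing causality will be considered as related". Missing intensity is kept as a category of its own.

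Neither document has a rule for a missing or partial AE start date.

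**The concern.** The start date decides whether an AE enters the treatment-emergent tables and in which period. AEs are recorded from consent (Protocol 8.6.2), so events before and after first dose share one database and the date has to separate them. If the date is absent or incomplete and may not be imputed, the event can fail the stated tests even when it did follow dosing.

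The error runs one way, because an event that cannot be placed is left out and reported toxicity falls. That is the opposite of the SAP's choice for missing causality. Treatment-emergent AEs are the safety endpoint (Protocol 8.5.5.6), and escalation cohorts are as small as 3 to 6 patients, so one omitted patient is visible in a cohort rate.

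**Working it through.** The documents give no figure on this point and no rate of missing dates. The check is therefore to apply the rules to each kind of incomplete date.

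**1. Start date wholly missing.** The period test needs a start date. Without one, neither inequality can be evaluated and 9.3.5 allows no substitute, so the AE belongs to no period. It also cannot be established that the AE began after first intake, so a literal program would send it to the remainder class ("otherwise it will be classified as non-TESS"). It is then absent from the TESS and by-period tables.

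**2. Month and year known, day missing: is it treatment-emergent?** If the first day of the known month is on or after first dose, the AE is treatment-emergent with no imputation. If first dose falls later in that same month, its status is ambiguous. Assumptions: first dose equally likely on each day of a 365-day year, cycles of exactly 21 days, onset equally likely on each day of the cycle. Day-by-day enumeration gives:

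| True onset in | Ambiguous | Still treatment-emergent |
|---|---|---|
| Cycle 1 | 63.8% | 36.2% |
| Cycle 2 | 6.3% | 93.7% |
| Cycle 3 | 0% | 100% |

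Hand check for Cycle 1 in a 30-day month. First dose on day 1 is never ambiguous. For days 2 to 10, all 21 onset days fall in the same month, which contributes 9. For days 11 to 30, the contribution is (20 + 19 + ... + 1)/21 = 210/21 = 10. The share is (9 + 10)/30 = 63.3%, in line with the enumeration. From Cycle 3 onset is at least 42 days after first dose, longer than any month, so nothing is ambiguous.

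**3. Month and year known: which period?** The whole month must lie inside the period. A month has 28 to 31 days and a cycle has 21. Adding the 3-day window that Protocol 8.5.1 allows from Cycle 2 gives 21 + 3 = 24, still below 28. No such date can be placed in a standard cycle. The exceptions are periods of at least 28 days: a cycle followed by a longer delay, or Cycle 1 running to end of study after discontinuation. For a final cycle after Cycle 1, the SAP defines the stop date by a next cycle that never starts, so placement there depends on how that gap is read.

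So a month-only AE can be known to be treatment-emergent and still have no place in tables built for each period. No all-periods TESS table is specified; the overall presentation in the quoted sentence reads most naturally as across cohorts.

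**4. Illustration of size (assumed rates).** Let p be the true share of patients with a given term, and m the share of those patients whose only event of that term is lost. The tabulated incidence is p × (1 − m). In a cohort of 6, the chance that at least one patient is lost is 1 − (1 − p·m)^6. With p = 50%:

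| m (assumed) | Tabulated incidence | Chance of at least one lost in 6 |
|---|---|---|
| 1% | 49.5% | 1 − 0.995^6 = 3.0% |
| 5% | 47.5% | 1 − 0.975^6 = 14.1% |
| 10% | 45.0% | 1 − 0.95^6 = 26.5% |

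Each lost patient lowers the cohort rate for that term by 1/6 = 16.7 points. A patient counts once per preferred term, so this happens only if no other counted event of the same term remains.

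**The case against.** The strongest reply is that the documents are silent on incomplete dates and do not state a harmful default. A reader might infer from "otherwise it will be classified as non-TESS" that the SAP deliberately sends undated events to the non-emergent class. The text does not support that: it is a general split between events that did and did not start or worsen after dosing. The loss under that split is a literal reading. The failure of the period test in step 1 is firmer, because that test explicitly needs a start date.

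Nor has 9.3.5 stopped field-level conventions elsewhere. Missing causality has a rule, planned times may replace unknown PK sampling times (Protocol 8.5.3), and values below the quantification limit are substituted (Protocol 9.3.2). So a date convention may be compatible with 9.3.5. This supports writing one; it does not supply one.

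Three further inferences are tempting and do not hold.

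- *Every partial date is lost from every treatment-emergent table.* Step 2 shows otherwise: a month wholly after first dose is enough for treatment-emergent status.
- *DLTs are lost and the MTD is affected.* DLTs are judged within Cycle 1, with inpatient monitoring to 48 hours and scheduled laboratory checks through Day 18, and several criteria require a measured duration. The Cohort Review Committee assesses all available data (Protocol 8.7), not TESS tables.
- *The events survive only in the general AE listing.* Serious AEs and grade ≥ 2 drug reactions have their own listings, and Protocol 9.3.4 promises AE incidence without a treatment-emergent restriction.

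The causality definitions also help. Certain, probable and possible each imply a plausible or reasonable time relation to dosing (Protocol 8.6.1.2), so such events have in effect been judged to follow drug. That judgement still does not provide the date that the period test needs.

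The data controls stand as a limit on size: 24-hour entry for serious AEs and 5 calendar days for others, electronic queries, 100% source verification and a pre-lock data review meeting. They cannot create an onset date that the source lacks, and Protocol 9.4 itself expects some queries to be outstanding at that meeting.

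**Conclusion.** The point holds in limited form. With no imputation and a period test that requires a start date, a wholly undated AE is left outside the treatment-emergent and by-period tables. Most month-only AEs cannot be assigned to a 21-day cycle, although those whose month lies wholly after first dose remain treatment-emergent. The direction is non-conservative and inconsistent with the SAP's own treatment of missing causality.

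The size cannot be computed. The 1% to 10% range above is an assumption, and the 64%, 6% and 0% shares rest on uniform first-dose and onset days. Given the data controls, the effect is probably small. It concerns the final safety report and is not shown to reach any DLT or MTD decision. It is worth correcting before database lock, because Protocol 9.5 treats analyses not pre-specified and run after lock as additional or exploratory.

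**What to change.** Add one rule to SAP 6.1.1.2 (Adverse Events), named as an exception to Protocol 9.3.5:

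- An AE with a missing or partial start date is treatment-emergent unless its known date parts or its end date show that it began before first dose without later worsening.
- If its period cannot be determined, show it in an undetermined-period row and include it in an all-periods TESS table. Do not force it into Cycle 1, which would inflate counts in the DLT window.
- Flag such events in the listings, so that a reader can count them.

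The cost is a short paragraph, one extra row and one extra table. The downside is that a few pre-treatment events may be counted as treatment-emergent; the listing flag makes these visible.

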9.4 PROTOCOL VIOLATIONS AND DATA REVIEW MEETING

Categories of protocol violations will be defined and will be integrated in the statistical analysis. a data review meeting (DRM) will take place at the end of the study in order to evaluate and accept the data management report, discuss remaining issues (outstanding queries, unresolved errors), and to confirm and approve relevant protocol violations. After this final DRM has taken place and the database is considered cleaned, the database will be locked.

9.5 STATISTICAL ANALYSIS PLAN

The SAP will be finalized before the lock of the study database. The SAP will describe in detail study endpoints and the statistical analyses, including the statistical analysis of the primary endpoint to be performed, including also additional endpoints and analyses not planned in the protocol. In case changes of the original primary endpoint or of the original primary analyses will occur during the study, these changes will be the subject of a substantial protocol amendment.

[figure not shown]
A Data Review Plan will be finalized before the start of the study. The Data Review Plan will describe the data that will be provided to the Investigators before every CRC meeting. All statistical analyses not pre-specified and run after data lock will be considered additional/exploratory analyses.

10. DATA QUALITY MANAGEMENT

10.1 DATA COLLECTION

Data collection activities will be carried out under the responsibility of the Sponsor. Patient data will be collected using an Electronic Data Capture system (EDC; see 10.1.1). Patients will be identified by the patient study identification number (patient ID), assigned during the Screening Period.

The patient ID will be a number composed of [REDACTED]

Data will be collected, processed, evaluated, reviewed and stored in anonymous form in accordance with applicable data protection regulations.

10.1.1 Case Report Forms

Clinical data collected during the study at sites will be recorded in an eCRF using [REDACTED] which is a validated system. The Sponsor will be responsible to develop the eCRF based on this study protocol and to review and perform the user acceptance test of the eCRF in order to ensure protocol adherence.

The eCRF will be made available to the study personnel by means of the [REDACTED] interface which is a validated system. The accounts will be individual and password-protected.

The Investigator or designee will be responsible for entering study data into the eCRF in accordance to the eCRF Completion Guidelines provided by the Sponsor. In order to improve the quality of data collection and cleaning, data shall be entered into the eCRF as closely as possible to the time when they become available and not later than within 5 working days. The eCRF data will not be considered as source data (the definition of the source data can be found in §10.3).

Investigators will ensure the accuracy, completeness, and consistency of data entered signing electronically the eCRF using the personal password.

An audit trail within the system will track all changes made to the data.

10.1.2 Central Laboratory/Examination data

The following Central Laboratories will be used during the study:

- [REDACTED]

- [REDACTED]
- [REDACTED]
- [REDACTED]
- [REDACTED]

Central laboratories data will be managed according to laboratory SOPs and will be transferred to Menarini Ricerche SpA - Clinical Sciences department for statistics and pharmacokinetics analyses. Sites will not receive reports from central laboratories.

Details on the collection, handling and shipment of samples will be provided in a separate Laboratory Manual supplied by the central laboratory [REDACTED] prior to the start of the study.

10.1.3 Data capture systems versions and validation documentation

Versions of the data capture systems can change during the study. The Sponsor will maintain a list of the data capture system versions used and the validation documentation of each version. The list and the validation documentation will be provided to the site at the site initiation visit (SIV) and will be updated at any data capture system version change.

10.2 CLINICAL DATA MANAGEMENT

Data Management will be carried out under the responsibility of the Sponsor.

The eCRF data will be electronically verified through the use of on-line and off-line checks. Discrepancies in the data will be resolved by means of electronic queries. Data will be locked by the data manager when all activities for the study, including medical revision of the data, are complete and no more entries are expected.

Data from sources other than the eCRF will be provided to the data manager on an agreed scheduled basis. The data manager has the responsibility to reconcile data captured in the eCRF, with external data sources. Discrepancies found in the reconciliation of the data, will be addressed by means of queries.

A clear overview of all clinical data management activities will be given in the data management plan.

10.3 SOURCE DATA

Source data are defined as all data in original records and certified copies of original records of clinical findings, observations or other activities in a clinical study that are necessary for the reconstruction and evaluation of the study.

Original documents and data records include, but are not limited to hospital/patients' medical records, laboratory notes, ECG records, patients' identification forms, and pharmacy dispensing records. Study sites will also maintain a paper drug accountability forms for the IMP to document dispensed and returned IMP patient.

Source data should be held available for perusal by the Sponsor representatives for the study or to other authorized persons such as auditors and inspectors of Regulatory Authorities.

Direct access to source data is defined as the permission to examine, analyze, verify and reproduce any records and reports that are important for evaluation of a clinical study (see Section 10.4.1). Any party allowed to direct access to study source data and documents should take all reasonable precautions within the constraints of the applicable regulatory requirements to maintain the confidentiality of patient identities and sponsor proprietary information.

Data should be consistent with the source documents and discrepancies, if any, should be explained in writing. All the original documentation pertinent to the study procedures must be available for review in each patient's record.

10.4 QUALITY CONTROL/QUALITY ASSURANCE

10.4.1 Study Monitoring

This study will be monitored in accordance with the ICH Note for Guidance on Good Clinical Practice. Monitoring will be carried out under the responsibility of the [REDACTED] The site monitor will perform visits to the study sites during the study conduct. Facilities, study drug, storage area, storage conditions for, immunogenicity, free CD205, PBMC isolation, eCRF, patient's source data, and all other study documentation will be inspected/reviewed by the site monitor for adherence to the protocol and Good Clinical Practice. At each site visit, the monitor will review the eCRFs for completion and accuracy. Accuracy will be checked by performing source data verification that is a direct comparison of the entries made onto the eCRFs against the appropriate source documentation. Any resulting discrepancies will be reviewed with the Investigator and his/her staff. The Investigator agrees to allow access to all study-related materials needed for the proper review of study conduct and to assist the monitor during the monitoring visits and during the data cleaning process. Monitoring procedures require that 100% of data are source data verified, particularly focusing on informed consents, adherence to inclusion/exclusion criteria, drug accountability, documentation of SAEs and the proper recording of efficacy and safety

measurements. All monitoring activities will be described in detail in the study-specific monitoring plan.

